#### 13.0 Withdrawal of Participants

- 13.1 Withdrawal Circumstances: Participants will be withdrawn from the study if they report any side effects of greater than moderate severity or that raise any safety concerns. Subjects may also be withdrawn from the study if they fail to follow study procedures (e.g., show up to scheduled study visits). Additionally, subjects will be told that participation is voluntary and that they may discontinue participation at any time for any reasons.
- 13.2 Withdrawal Procedures: Subjects who withdraw from the study after having received tDCS will be asked if they can be contacted by telephone to ascertain smoking status. We will attempt to contact subjects by telephone who do not show up to scheduled visit to ascertain if they wish to continue to participate in the study (and if not, why not) and to determine smoking status.

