#### 5.0 Procedures Involved

- **5.1** Study Design: This study is a randomized double-blind pilot study in which subjects will receive either active or sham tDCS
- **5.2** Study Procedures: The following procedures will occur during the study
- 5.2.1 Screening visit: Initial eligibility will be assessed via a phone interview. Those likely to qualify will be scheduled for a screening visit at which written informed consent will be obtained and eligibility confirmed. Medical, psychiatric and smoking history will be obtained via subject report with smoking status biochemically confirmed (via an exhaled carbon monoxide (CO) concentration of > 8 ppm or a urinary nicotine test strip = 6). Baseline levels of a variety of measures such as severity of smoking urges, severity of withdrawal symptoms, extent of nicotine dependence and how subjects evaluate their current cigarettes will be assessed via questionnaires. Height and weight will be measured. Those who qualify will be scheduled for a week during which they will come in daily for 5 consecutive days to receive tDCS treatments (active or sham) and will be asked to maintain a daily tobacco use diary in order to assess baseline levels of smoking. Subjects enrolled after revision # 3 has been approved and all preparations to enroll subjects into the scanning portion of the study are complete will be asked to come in for two additional visits to collect fMRI data: one visit before tDCS treatments begin, and a second visit after all tDCS treatments are completed.
- 5.2.2 MRI scanning visits (2 visits, 1 visit occurring during the week prior to and the other visit occurring during the week following the tDCS visits): Participants will undergo an MRI scan (3T), which takes about 75 to 80 minutes. MRI involves taking pictures of the participant's brain, from which the properties of certain brain tissues can be measured. These scans are strictly for research

purposes and therefore will not receive a clinical or medical interpretation. For the scan, the participant will be asked to lie down quietly on a bed, and the bed will slide into the scanner. Once the participant is inside the scanner, the imaging will begin. During the scan, the participant will be asked to lie quietly in the scanner with their eyes closed and may also be asked to perform a cognitive task (e.g., reversal learning task). The MRI scan will be performed at the University of Minnesota's Center for Magnet Resonance Research.

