At the beginning of each tDCS visit, participants will be assessed for number of cigarettes smoked 24 hours prior to the session, the time since last cigarette and exhaled CO levels. A cigarette evaluation scale will be completed at each visit. Additionally, adverse events, smoking urges and nicotine withdrawal symptom severity will be assessed before and after each session using several questionnaires. At the first tDCS session, urine will be collected to be analyzed at a later time for markers of cigarette smoking (e.g., cotinine concentrations). Prior to the first and after the last tDCS session, participants will also complete an impulsiveness questionnaire as this parameter is thought to be affected by tDCS, a

questionnaire assessing nicotine dependence as well as a questionnaire assessing motivation and self-efficacy to quit smoking.  Total participation time at each visit is not expected to exceed 2 hours per day.

At these visits, participants will be provided a smoking cessation treatment manual (Clearing the Air) and begin preparation for the quit date, which will be at the end of the 5th visit. The standardized content of the brief (10 min) behavioral treatment session provided to participants will include discussing benefits of quitting, ways to prepare the environment to minimize smoking cues (e.g., removing ashtrays), and methods to reduce craving and withdrawal symptoms (e.g., deep breathing). Participants will also keep track of situations associated with smoking and begin to develop a plan to deal with these situations.

This tDCS device to be used in this study is located in the MnDRIVE Non-invasive Neuromodulation Laboratory. There is currently no evidence of serious side-effects.  Mild side-effects that typically resolve upon discontinuing tDC include light itching under the electrode at the beginning of administration, headache, fatigue, and nausea. The subject may choose to discontinue stimulation at any time during the session if experiencing excessive discomfort or side effects. Although seizures are not a known risk of tDCS intervention,  anyone with a history or a risk for seizures will be excluded from the study. No other risks related to tDCS are anticipated.

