- 5.2.4 Post Cessation Visits (4 visits): Follow-up visits will occur at each of 4 weekly visits. At each visit, smoking diaries will be collected and exhaled CO will be measured. Urine will be collected at the week 1, 2 and 4 visits. Weight will be measured at week 1, 2, 3 and 4 visits. Questionnaire assessing craving and withdrawal symptoms severity will be assessed as will the effects that participants report from smoking (via the cigarette evaluation scale).
- **5.3** Individually Identifiable Health Information: All information is collected directly from subjects (i.e., medical records will not be requested) and this is not a treatment study. The data being collected therefore does not meet the definition of PHI.
- **5.4** Use of radiation: N/A
- **5.5** Use of Center for Magnetic Resonance Research: This study has been reviewed by the CMRR (Project Application Review System application # 5101)

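### Section 13.1 withdraws a subject with an above-moderate side effect from the whole study rather than from stimulation alone, so weekly secondary-outcome data are lost in a way tied to tolerability

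*Combined protocol and SAP*

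**What the plan says.** Section 13.1 makes withdrawal mandatory: "Participants will be withdrawn from the study if they report any side effects of greater than moderate severity". It applies the same consequence to side effects that raise a safety concern. Withdrawal for not following procedures, by contrast, is discretionary. The section has no route by which a subject stops stimulation and stays in follow-up.

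Section 5.2.3 shows that the protocol can separate the two: "The subject may choose to discontinue stimulation at any time during the session if experiencing excessive discomfort or side effects". It does not say that doing so means leaving the study.

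After withdrawal, 13.2 provides this: "Subjects who withdraw from the study after having received tDCS will be asked if they can be contacted by telephone to ascertain smoking status". It also plans calls to people who miss visits.

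The schedule that withdrawal cuts short is as follows.

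- **tDCS week (5.2.3):** "adverse events, smoking urges and nicotine withdrawal symptom severity will be assessed before and after each session using several questionnaires". Also, "Prior to the first and after the last tDCS session, participants will also complete an impulsiveness questionnaire". Participants "begin preparation for the quit date, which will be at the end of the 5th visit".
- **Weekly visits (5.2.4):** there are four. "At each visit, smoking diaries will be collected and exhaled CO will be measured". Craving, withdrawal and cigarette-evaluation questionnaires and weight are also collected, with urine at weeks 1, 2 and 4.
- **MRI (5.2.1):** scanned subjects have "a second visit after all tDCS treatments are completed".

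Section 11.1 continues recruitment until about 20 subjects complete. Section 16.0 plans linear mixed models for continuous outcomes and survival analysis for time to relapse. It states no analysis set, missing-data rule or censoring rule.

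**The concern.** Stopping stimulation is a sensible response to a bad reaction. Ending follow-up is a separate decision, and 13.1 makes both at once. The weekly visits consist of diaries, breath CO, urine, weight and questionnaires, so the documents give no evident safety reason to end them routinely.

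The subjects removed are those who tolerated stimulation worst. Their time to lapse and relapse, cigarette counts, craving and withdrawal scores after the quit date would be missing, or limited to smoking status from an optional call. Missingness of this kind could bias the secondary estimates, and 16.0 intends the pilot's effect sizes to inform larger studies. The rule also ends scheduled in-person contact with the people whose reactions a tolerability study most needs to follow.

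**Working it through.** The plan has no figure to reproduce: 16.1 says no power analysis was done, and no rate of above-moderate side effects is given. Section 14.1 lists only mild effects and calls adverse events rare. The rates below are assumptions.

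**1. What is kept and what is lost.**

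| Item | Subject withdrawn in the tDCS week |
|---|---|
| Triggering side effect | Kept (checked before and after each session) |
| Weekly CO, diary, craving and withdrawal assessments | 4 of each lost |
| Urine at weeks 1, 2 and 4 | 3 samples lost |
| Second MRI, if scanned | Lost |
| Smoking status | Possibly recovered by the 13.2 call |
| Quit date, if withdrawn before visit 5 | Not reached within the study |
| Impulsiveness questionnaire, if withdrawn before session 5 | Lost only if the last session is read as session 5 |

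**2. Number affected.** Let p be the chance that a treated subject has an above-moderate effect. Expected number = n × p. Chance of at least one = 1 − (1 − p)^n. Use n = 20 if both arms are at risk, and n = 10 if only the active arm is. The documents do not state the allocation ratio, so 10 per arm is an assumption.

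| p (assumed) | Expected of 20 | At least one of 20 | Expected of 10 | At least one of 10 |
|---|---|---|---|---|
| 1% | 0.2 | 18% | 0.1 | 10% |
| 2% | 0.4 | 33% | 0.2 | 18% |
| 5% | 1.0 | 64% | 0.5 | 40% |
| 10% | 2.0 | 88% | 1.0 | 65% |

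**3. Weekly visits lost by the time 20 complete.** If this is the only cause of loss and both arms are at risk, the expected number withdrawn is 20/(1 − p) − 20 = 0.202, 0.408, 1.053 and 2.222 at the four rates. At four visits each, that is 0.8, 1.6, 4.2 and 8.9 visits. With only an active arm at risk, and 10 completers needed in it, the figures halve.

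**4. Possible shift in a between-arm contrast.** If a fraction w of the active arm is missing and would have differed from the rest by D standard deviations, the completer mean is off by w × D. With w = 10% and D = 0.5 the shift is 0.10 × 0.5 = 0.05 SD. With w = 20% and D = 1.0 it is 0.20 × 1.0 = 0.20 SD. The standard error of a difference with 10 per arm is √(2/10) = 0.447 SD, so the shift is 0.05/0.447 = 0.11 to 0.20/0.447 = 0.45 standard errors. These values of w start at the top of the 1% to 10% range in step 2, so the illustration is generous. It also describes a plain completer comparison; a mixed model that uses data from before withdrawal may be affected less.

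**The case against.** The strongest reply is that the matter is small and partly handled. Section 13.2 follows directly from 13.1 and can recover smoking status, which bears on lapse and relapse. Above-moderate effects are expected to be rare, the outcomes are secondary, the trial is an unpowered pilot, and even generous assumptions move a contrast by less than half a standard error. All of that stands, and it is why the point is rated minor. But the call is optional and unscheduled, and it supplies no CO, craving, withdrawal or adverse-event data. Its wording speaks of subjects who withdraw, which may or may not include those withdrawn by the investigator.

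Several stronger readings are tempting, and the documents do not support them.

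- **That the primary tolerability endpoint is lost.** The triggering event is assessed around each session and so is recorded.
- **That 13.1 costs the remaining tDCS-week adverse-event checks.** These are tied to sessions, so stopping stimulation alone would end them too.
- **That the missingness is shown to be informative.** The link to tolerability is built into the rule, but nothing in the documents connects side effects with smoking, craving or impulsivity. Bias is possible, not demonstrated.
- **That the analysis is confined to completers.** Section 11.1 recruits to a number of completers, but 16.0 does not restrict the analysis to them.
- **That post-treatment impulsivity is necessarily lost.** The last session could mean the last one received.
- **That 13.1 removes scheduled weekly adverse-event data.** Section 5.2.4 lists no adverse-event question for any subject. That is a separate gap, which the monitoring group's procedures in section 18 may partly cover.

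**Conclusion.** The concern holds as a minor, cheap improvement. As written, 13.1 discards the four non-stimulation visits, and the second MRI where it applies, for any subject withdrawn in the tDCS week because of an above-moderate side effect. The expected number is 0.2 to 2.0 of 20 treated if both arms are at risk, or 0.1 to 1.0 if only an active arm of 10 is, at assumed rates of 1% to 10%. The consequence is possible bias in the secondary mixed-model and time-to-relapse estimates, and lost in-person contact with the worst-affected subjects. It does not threaten the pilot's main objective. The size rests on the assumed rates and on equal allocation; the fact that 13.1 ends the whole of participation rests on its text alone.

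**What to change.** Keep the safety trigger and change what follows it.

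1. **13.1:** the trigger stops tDCS. Consenting subjects stay in the four weekly visits unless attendance is unsafe, and the second MRI is done only if judged safe. They keep the planned quit date and complete the impulsiveness questionnaire when stimulation stops.
2. **13.2:** state that it also covers subjects withdrawn by the investigator, and ask about the adverse event at each contact until it resolves.

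The cost is one protocol and consent amendment, some staff time, and participant payments. Under 12.3 each visit pays $20, so a retained subject costs 4 × $20 = $80, or $100 with the second scan. Over the study, with both arms at risk, that is about 0.202 × $80 = $16 to 2.222 × $100 = $222. The $60 bonus requires attendance at all visits. It applies only if the subject also attends any remaining tDCS-week visits or the bonus rule is waived, and it raises the $80 and $100 to $140 and $160. A subject who attends remaining tDCS-week visits without stimulation would be paid a further $20 for each. These figures exclude scanner time and urine assays, which the study already plans for any subject who completes.

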## 14.0 Risks to Participants

**14.1** Foreseeable Risks: The device to be used in this study is a transcranial direct current stimulator - tDCS. tDCS is considered to be a safe brain stimulation technique that rarely results in adverse events. There is currently no evidence of serious side-effects. Mild side-effects that typically resolve upon discontinuing tDCS include light itching under the electrode at the beginning of administration, headache, fatigue, and nausea. The subject may choose to discontinue stimulation at any time during the session if experiencing excessive discomfort or sideeffects. Although seizures are not a known risk of tDCS intervention,  anyone with a history or a risk for seizures will be excluded from the study. No other risks related to tDCS are anticipated.

MRI risks: Individuals will complete a screening questionnaire for contraindications of MRI scanning which will be reviewed by CMRR staff at the University of Minnesota. A determination will be made regarding the level of risk to the subject and whether they are approved for scanning.

There are no known risks to humans due to the static magnetic field. Subjects, operators, and guests are screened prior to entering the magnetic environment,

and frequently reminded of the potential danger of introducing magnetic objects to the controlled area. Subjects are excluded from the study if they have any implanted devices. Subjects are always accompanied when near the magnet, and reminded to move slowly and carefully as they enter and leave the magnet.

The risk of tissue damage by energy emitted by the MRI device is controlled by compliance with FDA guidelines for commercial MRI devices. Safety devices are in place so that the magnet will cease to operate should any parameters begin to exceed their preset safety limits. The risk of peripheral nerve stimulation by dB/dt is limited by safety devices. The noise levels generated by each scan are monitored to ensure adherence to guidelines. In addition, subjects are provided with earplugs and secondary protection (foam covering or headphones) to increase comfort during the scan..

- **14.2** Reproduction Risks: There is limited data regarding the risks of tDCS to an embryo or fetus although since tDCS is a localized brain stimulation treatment, it is unlikely to have reproductive risks. The risks of MRI to fetuses are unknown. We will therefore exclude women who are pregnant or are planning to become pregnant during the study.
- **14.3** Risks to Others: There are no anticipated risks to others.

## **15.0** Potential Benefits to Participants

**15.1** Potential Benefits: As this is not a treatment study, there is no direct benefit to individual participants.

## 16.0 Data Management

Data Analysis Plan: Data collected in this pilot study will be used as preliminary data and proof of concept to facilitate the design of and estimate power for subsequent larger grants. Descriptive statistics will conducted and effect sizes will be estimated. Linear mixed models will be used to examine time, group (sham vs. active) and group by time effects for various continuous outcome measures (e.g. craving). Survival analyses will be used to examine group differences on time to relapse to smoking.

- **16.1** Power Analysis: As this is a pilot study, no power analysis was done.
- **16.2** Data Integrity: In order to ensure that data entry is correct, data collected on paper questionnaires will be entered twice with the two entries compared and any discrepancies resolved.

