# (if applicable)		
Study Population	medically stable smokers	
Sample Size (number of	20 to complete the study	
participants)		
Study Duration for Individual	Approximately 6 weeks	
Participants		

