fails to activate when required, as often observed in substance use disorder, target neurons in the NAcc core do not receive critical information needed to select the appropriate outcome, causing acquired maladaptive response patterns to persist (e.g. drug consumption). Higher FC between DLPFC and NAcc may be achieved by stimulating DLPFC while subjects perform tasks that require cognitive flexibility, an aspect of executive functioning.

Transcranial direct current stimulation (tDCS) has shown in both healthy subjects and in patients (e.g. Parkinson's disease, stroke, and depression) to modulate synaptic strengthening and neurotransmitter-dependent plasticity underlying changes in behavior and learning. It therefore has the potential to increase functional connectivity between NAcc and DLPFC when paired with a cognitive task engaging this pathway. As previously described, strengthening this pathway should facilitate proper selection of goal-directed behavior and decrease craving in those with substance use disorder.

There is currently limited data regarding the efficacy of tDCS on smoking cessation and no data regarding the efficacy of combining tDCS with a concurrent task requiring cognitive flexibility. Although studies have assessed the effect of tDCS on smoking behavior, these have not combined stimulation with a task requiring cognitive flexibility nor have these studies assessed cessation outcomes. Instead, smoking cues were presented either immediately prior to, during or immediately after neurostimulation with the outcomes assessed being either cue induced craving severity, number of cigarettes smoked during the days of stimulation or using laboratory based smoking choice paradigms. These studies have generally found small but positive effects in these measures. However by not combining tDCS with the cognitive flexibility task, these studies may not have been able to maximize the effects of this intervention.

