# 11.0 Local Number of Participants

11.1 Local Number of Participants to be Consented: We plan on recruiting subjects until approximately 20 have completed the study. We expect that as many as 50 subjects will undergo the consent process. Some of those that attend the screening visit will likely not meet inclusion / exclusion criteria whereas others will not be interested in participating.

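### Must section 16.0 say how effect sizes from about 20 completers will be turned into power for later trials?

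*Combined protocol and SAP*

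**What the plan says.** The Data Analysis Plan in section 16.0 is one short paragraph. It gives the use of the data as preliminary evidence, "to facilitate the design of and estimate power for subsequent larger grants", and continues: "Descriptive statistics will conducted and effect sizes will be estimated". It then names linear mixed models (time, group, group by time) for continuous outcomes and survival analysis for time to relapse. Section 16.1 adds: "As this is a pilot study, no power analysis was done".

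The design facts that set the precision are in other sections:

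- Section 11.1: "We plan on recruiting subjects until approximately 20 have completed the study"; the Study Summary agrees ("20 to complete the study").
- Section 5.1: "This study is a randomized double-blind pilot study in which subjects will receive either active or sham tDCS". No allocation ratio is given.
- Section 5.2.4: "Follow-up visits will occur at each of 4 weekly visits".
- Section 3.1 makes feasibility of recruitment and tolerability the primary endpoint. Smoking outcomes, craving and withdrawal are secondary.

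No section names the outcome whose effect size would be carried forward, attaches an interval to it, or states how it would become a sample size.

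**The concern.** Power for later grants and estimated effect sizes stand in adjacent sentences, so it is easy to assume that the observed difference will be entered into the next sample-size formula. That practice is known to be unreliable after a small pilot. An estimate that is too large by chance gives a trial that is too small, and estimates at or below zero usually lead to no trial, so the pilots that go forward tend to be the flattering ones. On average the later trial then has less power than it claims.

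Section 2.2 seems to make this worse, because it says of earlier tDCS studies in smokers: "These studies have generally found small but positive effects in these measures". The shortfall is largest when true effects are small. At stake would be the size of a future trial, and so the one use that section 16.0 names for these data.

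**Working it through.** There is no sample-size derivation in the documents to reproduce. Alpha, power, target effect, SD, allocation and event counts are not given. The following are therefore assumptions: 10 per arm, two-sided alpha 0.05, 80% power for the later trial, and effects in SD units.

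**Precision, simple two-group comparison.** The standard error is √(1/10 + 1/10) = 0.447. The half-width is 1.96 × 0.447 = 0.88 on the normal approximation, and 2.101 × 0.447 = 0.94 with t on 18 df. Unequal splits change little: on the normal approximation, 0.89 at 8:12 and 0.92 at 7:13.

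**Precision, repeated visits.** For the mean of four visits adjusted for baseline, with equal correlation r, the variance factor is (1 + 3r)/4 − r². The half-width is t (17 df, 2.110) × √(0.2 × factor).

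| r (assumed) | factor | half-width |
|---|---|---|
| 0.3 | 0.475 − 0.090 = 0.385 | 0.59 |
| 0.5 | 0.625 − 0.250 = 0.375 | 0.58 |
| 0.7 | 0.775 − 0.490 = 0.285 | 0.50 |

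This stands in for the planned mixed model. It is not the group-by-time model itself.

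**Time to relapse.** SE(log HR) = 2/√events, so the 95% factor is exp(1.96 × 2/√10) = 3.45 at 10 events and exp(1.96 × 2/√20) = 2.40 at 20. An observed hazard ratio of 0.60 would have an interval of 0.17 to 2.07 or 0.25 to 1.44. The event counts are assumed.

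**If the observed effect sized the next trial.** Pilots were simulated at 10 per arm with a small-sample-corrected d. The next trial's n per arm was set to 2(1.96 + 0.842)²/d², capped at 5,000, and its real power was taken from the noncentral t. A second go-rule, under which only estimates of at least 0.2 SD proceed, was also run. Neither go-rule is in the protocol. Mean real power against a nominal 80%:

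| Analysis in both trials | Go-rule | true d 0.2 | 0.3 | 0.5 | 0.8 |
|---|---|---|---|---|---|
| Simple comparison | any positive | 46% | 55% | 66% | 73% |
| Simple comparison | at least 0.2 | 27% | 43% | 61% | 71% |
| Four-visit mean, r = 0.5 | any positive | 58% | 66% | 73% | 75% |
| Four-visit mean, r = 0.5 | at least 0.2 | 36% | 54% | 70% | 74% |

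Repeat runs agree to within about one percentage point. At d = 0.3, the simple comparison needs 2 × 2.802²/0.09 = 174.4, so 175 per arm. The median planned size is 85 per arm if any positive estimate proceeds. In the four-visit, any-positive row, median real power is 79% at d = 0.5 and also at d = 0.8, so in that setting about half the later trials come close to target or exceed it.

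**What the text commits to.** Estimating power takes an SD, a within-subject correlation, a control-arm relapse rate and attrition as well as a target difference. Section 16.0 allows the pilot to supply all, some or none of these. Its wording does not select the observed difference as the target, and every cell in the table depends on that selection.

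**The case for a change.** The strongest case for a change is that section 16.0 itself claims this second use of the data, so calling the study a feasibility pilot does not remove the gap. No other section fills it, and the loss of power points the same way in every cell of the table. The remedy would be about three sentences, with no new data or visits. A commitment made before results are seen also cannot be shaped by a flattering estimate.

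Much of this stands: the omission is real, the imprecision is real, and the arithmetic reproduces. Three parts do not carry through to a change.

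- The step from silence to sizing on the point estimate is an inference. The protocol neither states nor implies a rule.
- The argument that small effects are the relevant range rests on one sentence of section 2.2. The next sentence there suggests that the earlier studies may have fallen short because they lacked the concurrent cognitive task. The same section says they did not assess cessation outcomes, and it gives no standardised effect.
- A sentence here forbidding use of the point estimate would try to bind a protocol that has not been written. That later protocol must justify its own target difference, and its reviewers can check it.

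**Conclusion.** No change to the plan follows. This is missing detail that competent analysts fill sensibly, and it leads to no wrong result in this study. Followed as written, the plan gives sound feasibility and tolerability findings and valid, though imprecise, effect estimates.

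The imprecision is a 95% half-width of about 0.94 SD for a simple comparison, or 0.50 to 0.59 SD for an adjusted four-visit mean, given a 10:10 split and correlations of 0.3 to 0.7. The shortfall in a later trial is hypothetical. If any positive estimate were used directly, mean real power would run from 46% to 75% over true effects of 0.2 to 0.8 SD, depending on the effect and the analysis. A stricter go-rule widens the range downwards to 27%. All of this assumes a sizing practice that the protocol does not adopt.

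Reporting each between-arm effect with its 95% interval is ordinary good practice and can be done within the existing wording. The pilot's SD, correlation, sham relapse rate and attrition are likewise useful to a later design, with their own uncertainty: on 18 df, the 95% limits of the SD run from 0.76 to 1.48 times the observed value. Neither step needs an amendment.
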